7.3 Excluded Medications and Dietary Products

Use of the agents in Table 3 (prescription or nonprescription) is prohibited from the time points specified until completion of all study activities

Table 3 Prohibited Medications and Dietary Products

28 days prior to Inpatient Check-in	14 days prior to Inpatient Check-in	7 days prior to Inpatient Check-in	72 hours prior to Inpatient Check-in	48 hours prior to Inpatient Check-in	24 hours prior to Inpatient Check-in
Nutraceuticals (e.g., St. John’s wort, ginseng, kava kava, ginkgo biloba, Chinese herbs, and melatonin) Immunization/ Vaccines ^(b) Known strong inhibitors/inducers of CYPs 3A4/5 ^(c)	Prescription medications ^(d) (including hormonal contraceptives ^(e))	OTC medications, including antacids, proton-pump inhibitors, and H2 receptor antagonists ^(a) Vitamin supplements Orexin receptor antagonists including suvorexant (Belsomra [®]), lemborexant (Dayvigo [®]), and related compounds	Nicotine-containing products Poppy seeds	Alcohol-containing products	Products containing caffeine or xanthine (e.g., tea or coffee)

CYP= cytochrome P-450, OTC=over the counter.

- (a) Occasional use of acetaminophen (~1 g/day) and 400mg ibuprofen TDS when required or other medication as approved by the sponsor's Medical Monitor on a case-by-case basis is allowed except on Day 1
- (b) Inclusive of but not limited to H1N1 and flu vaccinations. Subjects who have received the COVID-19 Vaccine between -10 and -28 days may participate, provided they did not experience any side effects of any description. COVID-19 vaccine doses may be administered 7 days post-study medication dosing.
- (c) e.g., chloramphenicol, clarithromycin, ketoconazole.
- (d) Certain prescription medications may be allowed on a case-by-case basis at the discretion of the Investigator and Sponsor.
- (e) Hormonal contraceptives are not permitted for female participants, as referenced in Table 3. Female partners of male participants can use hormonal contraceptives.

Subjects must be instructed not to take any medications during study participation, including over-the-counter drug products, without first consulting with the Investigator.

7.4 Diet, Fluid, Activity Control

Subjects will be confined to the clinic for each of the dosing days as well as a period of time sufficient to collect additional post-dose PK samples and monitor for safety and tolerability (Day -1 through Day 4 for single-dose cohorts and Day-1 through Day 9 for multiple-dose cohorts). During confinement, subjects will be provided 3 standard meals and a snack per day, each containing approximately 30% fat (relative to the total calories). The meals served on the day of dosing should be similar in nutritional content for each subject in the study. The study menu should be recorded and submitted to the study file with a copy provided to the sponsor following treatment. Breakfast will not be provided on dosing days until at least 4 hours after dose administration unless otherwise indicated (i.e., Days 2-6 for MAD cohorts). The meal start and stop times, and percentage of the meal consumed will be recorded in the source, and the appropriate electronic case report form (eCRF) for all meals served on dosing days.

If a blood draw or any study procedure coincides with a meal, the blood draw will take precedence, followed by the study procedure and then the meal.

Subjects will remain in bed at a semi-supine position for 4 hours following the dose administration, except as necessitated by the occurrence of an AE or study procedures (e.g., obtaining a 12-lead ECG). Subjects must refrain from strenuous exercise for 72 hours before Inpatient Check-in and until check-out.

On the dosing days where extensive PK and/or CSF sampling is indicated (i.e., single-dosing Day 1 and first and last multiple-dose days, e.g., days 1 and 7), CVN766 or placebo suspension will be administered with approximately 240 mL of water after a fast of at least 10 hours. Subjects will continue to fast for an additional 4 hours after dosing and eat lunch following the 4-hour PK blood and CSF collection. Subjects may consume water ad libitum except for 1 hour before and 1 hour after drug administration.

For the food effect cohort (S3), single-dose administration will be administered after ingesting a standardized high-fat, high-calorie meal according to FDA Guidance for Industry (Food-effect bioavailability and fed bioequivalence studies, Dec 2002). Subjects will finish at least approximately 85% of their breakfast within 30 minutes and will receive an investigational product 30 minutes (± 5 minutes) after beginning the meal. The S3 (food effect) cohort meals may be staggered to ensure dosing occurs 30 minutes after the beginning of the meal.

Subjects will also fast for at least 10 hours prior to safety laboratory collection times as indicated. However, consumption of water as desired is permitted during this time, except for dosing days, as indicated above.

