5.2 Endpoints

5.2.1 Primary Endpoints

- Percentage of subjects who experience at least one treatment-emergent adverse event (TEAE)
- Percentage of subjects with abnormal and clinically significant (CS) safety laboratory test results at least once post-dose
- Percentage of subjects with abnormal and CS electrocardiogram (ECG) test results at least once post-dose
- Percentage of subjects with abnormal and CS vital sign measurements at least once post-dose

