Screening	Inpatient Check-in	Dosing, PK, CSF, & Safety Assessments ^{a,f}	PK / Safety Assessments & inpatient discharge ^b	Follow-Up Outpatient Visits ^c	Follow-Up Call ^d
Day -28 to -2	Day -1	Days 1-7 ^e	1 and 2 days after last dose (e.g. Days 8-9)	3 days ±0 after last dose (e.g. Day 10) & 7 days ± 1 after last dose (e.g. Day 14)	14 days ±2 after last dose (e.g. Day 21)

- (a) CSF sampling is planned on Day 7 in Cohorts M1 and M2 (CSF sampling for Cohort M2 may be omitted at the discretion of the SRG). Cohort M3 also may, at SRG discretion, undergo PK sampling from CSF, the choice of day and sampling time to be decided by SRG.
- (b) Discharge from the clinic is planned for Day 9 but may be delayed for additional dosing days or if necessary, to continue monitoring for resolution of AEs.
- (c) If emerging PK data indicate the CVN766 $t_{1/2}$ is 15 hours (or less), the visit 3 days after the last dose (e.g., Day 10) may be omitted at Investigator’s discretion.
- (d) The Follow-up Visit will occur by telephone unless abnormal CS findings are observed upon discharge. In these cases, subjects must return to the clinic for re-evaluation.
- (e) Dosing duration may be increased to ≤14 days at the discretion of the SRG based on preliminary PK and projected time to steady-state.
- (f) Urine sampling will occur on Day1 and Day 7 in Cohort M1.

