9.1.12 Procedures for Clinical Laboratory Samples

All samples will be collected in accordance with acceptable laboratory procedures on the days/times stipulated in the Schedule of Study Procedures (**Appendix A**).

Table 10 lists the tests that will be obtained for each laboratory specimen.

Table 10 Clinical Laboratory Tests

Hematology	Serum Chemistry	Urinalysis
RBC	ALT	pH
WBC with differential (% and absolute)	Albumin	Specific gravity
Hemoglobin	Alkaline phosphatase	Protein
Hematocrit	Lipase (d)	Glucose
Platelets	AST	Blood
PT/INR	Total bilirubin	Nitrite
	Direct bilirubin	Microscopic Analysis
	Total protein	(only if positive dipstick results):
	Creatinine	RBC/high power field
	BUN/Urea	WBC/high power field
	Creatine kinase	Epithelial cells, casts etc.
	GGT	
	Potassium	
	Sodium	
	Glucose	
	Chloride	
	Bicarbonate	
	Calcium	
Diagnostic Screening:		
Serum	Urine/ Blood	
Serum hCG (a)	Drug screen including amphetamines (AMP), barbiturates (BAR), benzodiazepines (BZO), cannabinoids, cocaine (COC), opiates (OPI), alcohol, cotinine ^c methamphetamines, methadone (MET), methylenedioxymethamphetamine (MDMA), phencyclidine (PCP), tetrahydrocannabinol (THC)	
FSH (b)		
Hepatitis panel, including HBsAg and anti-HCV (e)		
Human Immunodeficiency Virus (HIV) antibody		
	Urine Pregnancy Test (a)	
	Alcohol (can be performed via breath test)	

FT4= free T4, FSH= follicle-stimulating hormone, GGT= γ -glutamyl transferase, hCG= human chorionic gonadotropin, PT=prothrombin time, RBC=red blood cells, TSH= thyrotropin, WBC=white blood cells.
 (a) Serum hCG pregnancy test will be done at Screening. Urine Pregnancy Test will be done at Check-in (Day -1).
 (b) FSH level will be obtained for female subjects at Screening if they are postmenopausal (i.e., last regular menstrual cycle >2 years) and not surgically sterile. The result must be >40 IU/L for the subject to be enrolled.
 (c) To be performed at Inpatient Check-in (Day -1).
 (d) To be performed on SAD Day -1 and 24- and 48-hours post-dose; and MAD fasting lipase tests will be performed on Day -1, Days 2,7 and 8 (predose).

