12.1.4.2 Clinical Laboratory Evaluation

Individual results of laboratory tests from hematology, chemistry, and urinalysis that are abnormal and CS will be summarized and listed. Baseline, post-dose, and change from baseline to post-dose laboratory data will be summarized for pooled placebo, each CVN766 dose level, and CVN766 overall. All clinical laboratory data will be listed.

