- (e) Record all ongoing medications from Screening and throughout the study.
- (f) Fasting clinical laboratory tests (hematology, serum chemistry, urinalysis) will be collected at Screening, Day -1, prior to dosing on Day 1, Days 2 through 4, Day 8, Early Termination (if applicable), and as appropriate at the Fasting lipase tests will be collected at Day -1, 24 hours and 48 hours post-dose. An additional tube (for blood serum) will be obtained on Day -1 and Day 2, and the collected serum will be stored at -70C to enable additional, retrospective analyses as needed.
- (g) A FSH level will be obtained on post-menopausal women (defined as continuous amenorrhea of at least 2 years and not surgically sterile).
- (h) Triplicate standard 12-lead ECG will be recorded at Day 1 (pre-dose [within 1 hour prior to dosing], and at 0.5, 1, 2, 4-, 6-, 8-, and 12-hours post-dose), and then every 12 hours until 48 hours post-dose, Day 4, Day 8, Early Termination (if applicable) .
- (i) One blood sample will be collected for pharmacogenomic analysis prior to dosing on Day 1; this will only be collected once per subject.
- (j) Whole blood samples will be collected on Day 1 (pre-dose, 8-, and 24-hours post-dose) for RNA pharmacogenomic analysis. Samples will also be collected during the food effect period.
- (k) Blood samples for PK analyses will be collected at time points indicated in Table 6.
- CSF samples (up to 10 mL) will be collected at 3 h post-dose by lumbar puncture only in selected cohorts as indicated in Table 9.
- (l) PTEs will be collected from signing of informed consent up until dosing on Day 1.
- (m) Any AE with onset or exacerbation after dosing on Day 1 will be captured as an AE.
- (n) CV telemetry should be recorded at least 12 hours prior to dosing, and up to 24 hours after dosing
- (o) Neurological exam to consist of light touch, power in limbs, and brief cranial nerve examination.

Cohort 3 SAD Fasted-Fed Crossover	Screening	Dosing and Observation Inpatient					D/C	Inpatient No sooner than +14 days or 4 half- lives of Day 8 visit					+4 days post D/C	E/T	F/U Day 14 (±2) (b)
		Days -28 to -2	Day -1	Day 1	Day 2	Day 3		Day 4	Day 8	Day -1	Day 1	Day 2			
Informed consent	X														
Inclusion/exclusion criteria	X	X													
Admitted to the Clinic		X													
Demographics and medical history	X														
Medication history	X							X							
Neurological Exam (o)		X	X	X	X	X		X	X	X	X	X			
Physical examination	X	X				X	X	X				X	X	X	

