Physical examination	X	X	X						X		X		X	X	
Vital signs (c)	X	X	X	X	X	X	X	X	X	X	X		X	X	
Weight, height, and BMI (d)	X	X	X						X		X		X	X	
Urine drug screen	X	X													
Cotinine screen		X													
Concomitant medications (e)	X	X	X	X	X	X	X	X	X	X	X	X	X	X	X
Concurrent medical conditions	X	X													
Clinical laboratory tests (f)	X	X	X	X	X	X	X	X	X	X	X		X	X	X
Hepatitis panel and HIV antibody test	X														
FSH (g)	X														
Serum Pregnancy test (hCG)	X														
Urine Pregnancy Test		X													
ECG (h)	X	X	X	X	X	X	X	X	X	X	X		X	X	

Multiple-Dose Regimen Cohorts	SCR	Check -in	Inpatient Dosing & Observation							Inpatient Discharge (a)	Outpatient Visit		E/T	Follow-up
			Day 1	Day 2	Day 3	Day 4	Day 5	(model for additional dosing days) Day 6	Day of last dose (e.g. Day7)		1 day after last dose (e.g. Day 8)	2 days after last dose (e.g. Day 9)		
Study Day:	Days -28 to -2	Day -1												
PGx DNA sample collection (i)			X											
PGx RNA collection (j)			X						X					
PK blood collection (k)			X	X	X	X	X	X	X	X	X	X	X	X
Study drug dosing			X	X	X	X	X	X	X					
PTE assessment (l)	X	X	X											
AE assessment (m)			X	X	X	X	X	X	X	X	X	X	X	X

PGx=pharmacogenomic (a) Events listed as occurring at “Inpatient Discharge” visit will occur on that day prior to formal “Inpatient Discharge” but not necessarily at the time of Discharge.
 (b) The Follow-up Visit will occur by telephone on Day 21 (±2) unless abnormal CS findings are observed upon discharge. In these cases, subjects must then be brought back to the clinic for re-evaluation per Investigator’s discretion.
 (c) Vital signs (tympenic body temperature, respiration, pulse, and blood pressure) will be obtained at Screening, Inpatient Check-in (Day -1), Day 1 and Day 7 (pre-dose [within 1 hour and 30 minutes prior to dosing], and at 1, 2, 4-, 6-, 8-, and 12-hours post-dose), Days 2 through 6 (pre-dose and 12 hours post-dose), Day 8, Day 9, Early Termination (if applicable), and as appropriate at the Follow-up Visit Day 14 (±2 days). Triplicate orthostatic vital signs (blood pressure and heart rate) will be recorded at baseline (Check-in Day-1) 15 minutes apart.
 (d) Height and BMI will be collected at Screening only.
 (e) Record all ongoing medications from Screening and throughout the study.

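### The exercise ban ends at check-out, so CK, AST and ALT at the outpatient visits are drawn without the 72-hour restriction that covers the baseline draws

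*Protocol*

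**What the plan says.** References are to the amended protocol; the preceding version has the same exercise rule.

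- **Exercise rule.** Section 7.4: "Subjects must refrain from strenuous exercise for 72 hours before Inpatient Check-in and until check-out". The same section gives the confinement period as "Day -1 through Day 4 for single-dose cohorts and Day-1 through Day 9 for multiple-dose cohorts". No other section restricts exercise after discharge.
- **What is measured.** Table 10 in Section 9.1.12 lists "Creatine kinase" in the serum chemistry panel, together with ALT and AST.
- **When it is measured, single dose.** Footnote (f) of the Appendix A schedule places laboratory tests at Screening, at Day -1 and then "prior to dosing on Day 1, Days 2 through 4, Day 8, Early Termination (if applicable". Table 1 gives the outpatient visit as Day 8 ±1 day. The S3 grid adds a draw 4 days after fed discharge.
- **When it is measured, multiple dose.** Table 2 in Section 6.1.2 places the outpatient visit at "7 days ± 1 after last dose (e.g. Day 14". The Appendix A grid marks laboratory tests at that visit and at follow-up. Footnote (f) of that grid names Day 9, Early Termination and, as appropriate, Day 21, but not Day 14.
- **How the results are used.** A primary endpoint in Section 5.2.1 is "Percentage of subjects with abnormal and clinically significant (CS) safety laboratory test results at least once post-dose". Section 12.1.4.2 adds: "Baseline, post-dose, and change from baseline to post-dose laboratory data will be summarized". Section 6.3.1 has study-level hold rules based on ALT/AST multiples.

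**The concern.** The baseline chemistry (Day -1 and pre-dose Day 1) is drawn after at least 72 h without strenuous exercise. The outpatient chemistry is drawn after a period in which exercise is free. If exercise raises CK, AST or ALT, a late rise has an ordinary explanation that the design leaves uncontrolled, and the comparison with baseline mixes two sampling conditions.

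The results carry weight. The primary laboratory percentage has no cut-off at discharge. Section 9.1.12 requires every clinically significant laboratory abnormality to be recorded as an event, so one late post-dose result can count in both the adverse-event and the laboratory primary endpoints. In Section 6.3.1, hold rule 2 (two or more subjects with ALT/AST above 5×ULN) and hold rule 4 (two or more subjects with ALT/AST above 3×ULN plus listed symptoms, fatigue among them) have no time window and no exemption for another cause; rule 3 has such an exemption. The protocol does carry other controls through to these visits: Section 7.4 requires a 10-hour fast before safety laboratory draws, and Section 7.3 keeps alcohol and caffeine prohibited until all study activities are complete.

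**Working it through.** The protocol states no figure to reproduce here; the check is visit-day arithmetic.

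**1. Discharge-to-visit gap** = (outpatient day ± window) − check-out day, in nominal whole days.

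| Cohorts | Check-out | Outpatient draw | Gap | Hours |
|---|---|---|---|---|
| Single dose | Day 4 | Day 8 ±1 | 7−4 to 9−4 = 3–5 days | 72–120 |
| S3, fed period | fed Day 4 | 4 days after discharge | 4 days | 96 |
| Multiple dose | Day 9 | Day 14 ±1 | 13−9 to 15−9 = 4–6 days | 96–144 |

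The gap is at least 72 h in every row, so an interval as long as the one restricted before check-in is unrestricted before these draws. At the single-dose lower bound it equals 72 h and does not exceed it. Clock times of discharge and draw are not fixed, so that bound is approximate.

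**2. Share of draws affected.** In a single-dose period the scheduled post-dose draws are Days 2, 3, 4 and the outpatient visit, so 1 of 4 is unrestricted. In multiple-dose cohorts, the draws through Day 9 are restricted. The Day 14 draw, and any Day 21 draw (Day 21±2 minus Day 9 = 10–14 days after discharge), are not.

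**3. Weight of one result.** With 6 active subjects per dose level, one clinically significant result moves that level's percentage by 1/6 = 16.7 points. This holds for an event of any cause; it describes the cohort size, not the exercise effect.

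**4. Hold rule 2, illustration only.** The protocol gives no rate p of exercise-related ALT/AST above 5×ULN. For assumed p, P(at least 2 of n) = 1 − (1−p)^n − n·p·(1−p)^(n−1).

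| Assumed p | n = 8 (one cohort) | n = 64 (all planned subjects) |
|---|---|---|
| 0.5% | 0.07% | 4.1% |
| 1% | 0.3% | 13.5% |
| 2% | 1.0% | 36.7% |
| 5% | 5.7% | 83.6% |

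The range is too wide to support any size for the effect. It shows only that a rule counting across cohorts is more exposed to background elevations than one counting within a cohort.

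**The case against.** The strongest case on the other side is that this is a choice with modest consequences and not an error. Much of it stands.

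- **Purpose.** Section 7.4 never says that the ban protects laboratory values; that is an inference. Screening draws (Day -28 to -2) have no exercise rule of their own, yet ALT/AST at Screening decides eligibility, with repeat testing as the safeguard. A reader might infer that the protocol contradicts its own standard for valid laboratory results. It sets no such standard, and no two passages on exercise conflict.
- **Filters.** The primary endpoint needs the investigator to call a result clinically significant, and an explained, isolated CK rise need not qualify. ALT/AST above 3×ULN prompts repeat tests within at most 7 days, and the liver-test AE rule in Section 9.8.3 needs two consecutive elevations. These filters are partial: the change-from-baseline summaries and the threshold in hold rule 2 do not depend on that judgement.
- **Direction.** A reader might infer bias in favour of placebo or against the drug. Treatment is randomised and blinded, and exercise after discharge is not expected to differ by arm, so the result is noise. Placebo is also pooled within each part: 5×2 = 10 single-dose and 3×2 = 6 multiple-dose subjects, not 2.
- **Dosing decisions.** The minimum data for escalation (72 h after a single dose, 48 h after the seventh dose) are all collected in confinement under the ban. The individual liver criteria in Section 7.5 apply only during treatment. CK is in no hold rule, and a triggered hold leads to review by the Safety Review Group, not to automatic termination.

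What remains is that the outpatient draws count in the analysis and in Section 6.3.1 as written, and an analysis plan cannot restore a sampling condition that was not controlled.

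**Conclusion.** The gap is real and small in kind: baseline chemistry is drawn under a 72 h exercise restriction, and the outpatient chemistry is drawn after 72–120 h (single dose) or 96–144 h (multiple dose) without one. It can add non-differential noise and false positives to the primary laboratory percentage, the change-from-baseline summaries and hold rules 2 and 4 of Section 6.3.1.

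This rests on two assumptions: that strenuous exercise can raise these enzymes enough to matter, which the protocol does not quantify, and that some subjects exercise after discharge. The size cannot be computed. Neither a systematic drug effect nor a likely dosing hold follows from the protocol, and the upper figures in the illustration should not be read as a forecast.

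Two neighbouring texts need reconciling whatever is decided on exercise. The multiple-dose grid marks a laboratory draw 7 days after the last dose, but its footnote (f) omits Day 14. Section 6.1.3 evaluates adverse events against the Section 6.3.1 criteria up to discharge, while Section 6.3.1 itself sets no window.

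Rating: cheap improvement, optional.

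**What to change.** Add one sentence to Section 7.4, and to the subject instructions: subjects also refrain from strenuous exercise for 72 h before each scheduled outpatient laboratory visit. This covers Day 8 in single-dose cohorts, the visit 4 days after fed discharge in S3, the visit 7 days after the last dose in multiple-dose cohorts, and Day 21 where a laboratory draw is planned. The 72 h fits within every nominal discharge-to-visit gap.

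The cost is about 3 extra days of activity restriction per outpatient laboratory visit, so about 6 days in S3. No visit, sample or dose changes.

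A continuous ban until the last draw is not advised. In multiple-dose cohorts it could run from Day 9 to Day 21, 12 days. In S3 it would run at least from Day 4 to Day 22, 18 days: fed dosing no sooner than Day 15 under Section 6.1.1, fed discharge 3 days later on Day 18, and the visit 4 days after that.

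In the same amendment, align footnote (f) of the multiple-dose schedule with its grid.

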7.5 Criteria for Discontinuation or Withdrawal of a Subject

The primary reason for discontinuation or withdrawal of the subject from the study or study medication should be recorded in the eCRF using the following categories. For screen failure subjects, **Section 9.1.15**.

1. The subject has experienced a PTE or AE that requires early termination because continued participation imposes an unacceptable risk to the subject's health or the subject is unwilling to continue because of the PTE or AE.
2. Liver Function Test (LFT) Abnormalities

Study medication should be discontinued immediately with appropriate clinical follow-up (including repeat laboratory tests until a subject's laboratory profile has returned to normal/baseline status) if the following circumstances occur at any time during study medication treatment:

- ALT or AST $>8 \times$ ULN, or
 - ALT or AST $>5 \times$ ULN and persists for more than 2 weeks, or
 - ALT or AST $>3 \times$ ULN in conjunction with elevated total bilirubin $>2 \times$ ULN or INR >1.5 , or
 - ALT or AST $>3 \times$ ULN with the appearance of fatigue, nausea, vomiting, right upper quadrant pain or tenderness, fever, rash and/or eosinophilia ($>5\%$).
3. Significant protocol deviation. The discovery post-randomization that the subject failed to meet protocol entry criteria or did not adhere to protocol requirements and continued participation poses an unacceptable risk to the subject's health.
 4. Lost to follow-up. The subject did not return to the clinic, and attempts to contact the subject were unsuccessful. Attempts to reach the subject must be documented.
 5. Voluntary withdrawal. The subject (or subject's legally acceptable representative) wishes to withdraw from the study. The reason for withdrawal, if provided, should be recorded in the eCRF.

Note: All attempts should be made to determine the underlying reason for the withdrawal, and, where possible, the primary underlying reason should be recorded (i.e., withdrawal due to an AE).

6. The sponsor, IRB, IEC, or regulatory agency terminates the study.
7. Other.

Note: The specific reasons should be recorded in the “specify” field of the eCRF.

